5.5 Diet/Activity/Other Considerations

5.5.1 Diet

Subjects should maintain a normal diet unless modifications are required to manage an AE such as diarrhea, nausea or vomiting.

5.5.2 Contraception

Pembrolizumab and/or cabozantinib may have adverse effects on a fetus in utero. Animal reproduction studies have not been conducted with pembrolizumab; however, blockade of PD-L1 signaling has been shown in murine models of pregnancy to disrupt tolerance to the fetus and to result in an increase in fetal loss. These results indicate a potential risk, based on its mechanism of action, that administration of pembrolizumab during pregnancy could cause fetal harm, including increased rates of abortion or stillbirth. Human IgG4 is known to cross the placental barrier and pembrolizumab is an IgG4; therefore, pembrolizumab has the potential to be transmitted from the mother to the developing fetus. Pembrolizumab is not recommended during pregnancy unless the clinical benefit outweighs the potential risk to the fetus.

Furthermore, it is not known if pembrolizumab and/or cabozantinib have transient adverse effects on the composition of sperm.

For this trial, male subjects will be considered to be of non-reproductive potential if they have azoospermia (whether due to having had a vasectomy or due to an underlying medical condition).

Female subjects will be considered of non-reproductive potential if they are either:

(1) Postmenopausal (defined as at least 12 months with no menses without an alternative medical cause; in women < 45 years of age a high follicle stimulating hormone (FSH) level in the postmenopausal range may be used to confirm a post-menopausal state in women not using hormonal contraception or hormonal replacement therapy. In the absence of 12 months of amenorrhea, a single FSH measurement is insufficient.);

OR

(2) Have had a hysterectomy and/or bilateral oophorectomy, bilateral salpingectomy or bilateral tubal ligation/occlusion, at least 6 weeks prior to screening;

OR

(3) Have a congenital or acquired condition that prevents childbearing.

Female and male subjects of reproductive potential must agree to avoid becoming pregnant or impregnating a partner, respectively, while receiving study drug and for 120 days after the last dose of study drug by complying with one of the following:

(1) Practice abstinence[†] from heterosexual activity;

OR

(2) Use (or have their partner use) acceptable contraception during heterosexual activity.

Acceptable methods of contraception are[‡]:

Single method (one of the following is acceptable):

- Intrauterine device (IUD)
- Vasectomy of a female subject's male partner
- Contraceptive rod implanted into the skin

Combination method (requires use of two of the following):

- Diaphragm with spermicide (cannot be used in conjunction with cervical cap/spermicide)
- Cervical cap with spermicide (nulliparous women only)
- Contraceptive sponge (nulliparous women only)
- Male condom or female condom (cannot be used together)
- Hormonal contraceptive: oral contraceptive pill (estrogen/progestin pill or progestinonly pill), contraceptive skin patch, vaginal contraceptive ring, or subcutaneous contraceptive injection

†Abstinence (relative to heterosexual activity) can be used as the sole method of contraception if it is consistently employed as the subject's preferred and usual lifestyle and if considered acceptable by local regulatory agencies and ERCs/IRBs. Periodic abstinence (e.g., calendar, ovulation, sympto-thermal, post-ovulation methods, etc.) and withdrawal are not acceptable methods of contraception.

‡If a contraceptive method listed above is restricted by local regulations/guidelines, then it does not qualify as an acceptable method of contraception for subjects participating at sites in this country/region.

Subjects should be informed that taking the study medication may involve unknown risks to the fetus (unborn baby) if pregnancy were to occur during the study. In order to participate in the study subjects of childbearing potential must adhere to the contraception requirement (described above) from the day of study medication initiation (or 14 days prior to the initiation of study medication for oral contraception) throughout the study period up to 120 days after the last dose of trial therapy. If there is any question that a subject of childbearing potential

will not reliably comply with the requirements for contraception, that subject should not be entered into the study.

5.5.3 Use in Pregnancy

If a subject inadvertently becomes pregnant while on treatment with pembrolizumab and/or cabozantinib, the subject will immediately be removed from the study. The site will contact the subject at least monthly and document the subject's status until the pregnancy has been completed or terminated. The outcome of the pregnancy will be reported to the Sponsor-Investigator without delay and within 24 hours and within 2 working days to Merck if the outcome is a serious adverse experience (e.g., death, abortion, congenital anomaly, or other disabling or life-threatening complication to the mother or newborn).

The investigator will make every effort to obtain permission to follow the outcome of the pregnancy and report the condition of the fetus or newborn to the Sponsor-Investigator. If a male subject impregnates his female partner the study personnel at the site must be informed immediately and the pregnancy reported to the Sponsor-Investigator and to Merck and followed as described above and in Section 7.7.

5.5.4 Use in Nursing Women

It is unknown whether pembrolizumab or cabozantinib are excreted in human milk. Since many drugs are excreted in human milk, and because of the potential for serious adverse reactions in the nursing infant, subjects who are breast-feeding are not eligible for enrollment.

5.6 Subject Withdrawal/Discontinuation Criteria

5.6.1 Subject Withdrawal

Subjects may withdraw consent at any time for any reason or be taken off study treatment at the discretion of the investigator should any untoward effect occur. In addition, a subject may be withdrawn by the investigator or the Sponsor if enrollment into the trial is inappropriate, the trial plan is violated, or for administrative and/or other safety reasons.

5.6.2 Subject Discontinuation

A subject must be discontinued from the taken off study treatment for any of the following reasons:

• The subject or legal representative (such as a parent or legal guardian) withdraws consent.

• Confirmed radiographic disease progression

Note: A subject may be granted an exception to continue on treatment with confirmed radiographic progression if clinically stable or clinically improved, provided they meet all criteria for treatment beyond progression and have approval of the Principal Investigator (Section 5.7)

- Unacceptable adverse experiences as described in Section 5.2.1.2, 5.2.1.3, 5.2.1.3.1, and 5.2.1.3.2.
- Intercurrent illness that prevents further administration of treatment
- Investigator's decision to withdraw the subject
- The subject has a confirmed positive serum pregnancy test
- Noncompliance with trial treatment or procedure requirements
- The subject is lost to follow-up
- Administrative reasons

5.6.3 Clinical Criteria for Early Trial Termination

Early trial termination will be the result of the criteria specified below:

- Quality or quantity of data recording is inaccurate or incomplete.
- Poor adherence to protocol and regulatory requirements.
- Incidence or severity of adverse drug reaction in this or other studies indicates a potential health hazard to subjects.
- Plans to modify or discontinue the development of the study drug.

In the event of Merck's decision to no longer supply study drug, ample notification will be provided so that appropriate adjustments to subject treatment can be made.

Specific details regarding the procedures to be followed due to subject discontinuation or withdrawal from the study are provided in Section 7.1.4 – Other Procedures – Withdrawal/Discontinuation.

The End of Treatment/ Follow-up visit procedures are listed in Section 6 (Trial Schedule of Events) and Section 7.1.5 (Visit Requirements). After the end of treatment, each subject will be followed for 30 days for adverse event monitoring (serious adverse events will be collected

for 90 days after the end of treatment as described in Section 7.2.5.3). Subjects who discontinue treatment for reasons other than progressive disease will have post-treatment follow-up for disease status until disease progression, initiating a non-study cancer treatment, withdrawing consent or becoming lost to follow-up.

5.7 Treatment Beyond Disease Progression

Subjects may continue study treatment after standard RECIST v1.1 criteria for progressive disease are met provided they meet all the following criteria:

- Absence of symptoms and signs (including worsening of laboratory values, e.g., new or worsening hypercalcemia) indicating unequivocal progression of disease.
- Eastern Cooperative Oncology Group (ECOG) performance status 0 or 1.
- Absence of tumor progression at critical anatomical sites such as the central nervous system, central airway, the great vessels, and other organs or tissues where tumor progression would be expected to result acutely in severe and/or irreversible disability or death.
- Subjects must provide written consent to acknowledge discussion with the treating investigator of the benefit-risk balance of continuing study treatment beyond radiographic progression.
- If radiographic disease progression is confirmed at a subsequent tumor assessment, subjects may be considered for continued study treatment at the investigator's discretion after discussion with the Principal Investigator, if they continue to meet the criteria above and have evidence of clinical benefit, as evidenced by improvement in one or more symptoms or signs attributable to the underlying cancer.

5.8 Subject Replacement Strategy

Any dose-escalation subject who does not complete the DLT assessment window for a reason other than a DLT will be considered non-evaluable for dose escalation decisions, as well as, the MTD and RP2D assessment and may be replaced by an additional subject at that same dose level.

A subject who has any component of study treatment held during the DLT assessment window for a reason other than a DLT such that administration of the next planned pembrolizumab dose is delayed by more than 7 days and/or $\geq 25\%$ of the planned cabozantinib doses are missed, will be considered non-evaluable for dose-escalation decisions and the MTD assessment and may be replaced by an additional subject at that same dose level.

5.9 Known Potential Benefits

The risks to subjects are reasonable in relation to the anticipated benefits to subjects and/or society, and in relation to the importance of the knowledge that may reasonably be expected to result, thereby falling in favor of performing the study:

- To Participant: Potential benefit of improved efficacy of the combination of cabozantinib and pembrolizumab.
- To Society: Potential benefit of establishing benefit of this combination as a treatment option to future patients with metastatic renal cell carcinoma.

Justify the importance of the knowledge gained: While there are survival benefits of cabozantinib monotherapy and nivolumab (an anti-PD-1 antibody similar to pembrolizumab currently approved for metastatic renal cell carcinoma) monotherapy, these treatments are not curative and resistance develops. The hope is that the combination would provide lead to more response rates and slower resistance to treatment, compared to each agent alone.

6.0 TRIAL SCHEDULE OF EVENTS CHART

| Trial Period: | Trial Period: Screening Treatment Cycles ^a | | | | | | | End of Treatment/ Follow Up Visit | Survival Follow-Up ^m | |
|--|---|----|---------|---------|---------|----------|-----------------------|--------------------------------------|---|------------------|
| | Main Study | | | | | Te be | o be repe yond 7 c | ated ycles | Safety Follow-up | Overall Survival |
| Treatment Cycle/Title: | Screening | 1 | 2 | 3 | 4 | 5 | 6 | 7 | | Every 6 months |
| Scheduling Window (Days): | -28 to -1 | | ± 3 | ± 3 | ± 3 | ± 3 | ± 3 | ± 3 | Within 30 days post treatment discontinuation | ± 1 month |
| Informed Consent | Х | | | | | | | | | |
| Inclusion/Exclusion Criteria | Х | | | | | | | | | |
| Demographics and Medical History | Х | | | | | | | | | |
| Prior and Concomitant Medication Review | Х | Х | Х | Х | Х | Х | Х | Х | Х | |
| Pembrolizumab Treatment Administration ¹ | | Х | Х | Х | Х | Х | Х | Х | | |
| Cabozantinib Treatment Administration | | Х | Х | Х | Х | Х | Х | Х | | |
| Post-study Anticancer Therapy Status | | | | | | | | | Х | |
| Survival Status ^m | | | | | | | | | Х | X ^m |
| Review Adverse Events | Х | Х | Х | Х | Х | Х | Х | Х | Х | |
| Full Physical Examination | Х | Х | Х | Х | Х | Х | Х | Х | Х | |
| Vital Signs and Weight | Х | Х | Х | Х | Х | Х | Х | Х | Х | |
| Height | Х | | | | | | | | | |
| ECOG Performance Status | Х | Х | Х | Х | Х | Х | Х | Х | Х | |
| 12-lead EKG | Х | | | | Х | | | X ^k | Х | |
| Pregnancy Test – Urine ^b | Х | Xj | Х | Х | Х | Х | Х | Х | | |
| PT/INR, aPTT, LDH | Х | | | | | | | | | |
| CBC with Differential | Х | Xj | Х | Х | Х | Х | Х | Х | Х | |
| Comprehensive Serum Chemistry Panel, including Phosphorus | Х | Xj | Х | Х | Х | Х | Х | Х | X | |
| Urinalysis | Х | Xj | Х | Х | Х | Х | Х | Х | Х | |
| Total T3, Free T4, and TSH ⁱ | Х | | | | Х | | | Х | Х | |

| Trial Period: | Screening | Treatment Cycles ^a | | | | | End of Treatment/ Follow Up Visit | Survival Follow-Up ^m | | |
|---|----------------------------|-------------------------------|-----|-----|-----|-----------------------------------|--------------------------------------|------------------------------------|---|-----------------|
| | Main Study Screening | | | | | To be repeated beyond 7 cycles | | ed cles | Safety Follow-up | Overall Surviva |
| Treatment Cycle/Title: | (Visit 2) | 1 | 2 | 3 | 4 | 5 | 6 | 7 | | Every 6 months |
| Scheduling Window (Days): | -28 to -1 | | ± 3 | ± 3 | ± 3 | ± 3 | ± 3 | ± 3 | Within 30 days post treatment discontinuation | ±1 month |
| Tumor Imaging ^e (CT or MRI C/A/P +/- Whole Body Bone Scan ^d) | х | | | | X | | | х | | |
| RECIST 1.1 and irRECIST radiology read ^c | Х | | | | Х | | | Х | | |
| Archival Tumor Collection | Х | | | | | | | | | |
| Optional Fresh Tumor Biopsies (baseline and post-treatment) | Xe | | Xe | | | | | | | |
| • PD-L1 Testing | Х | | Х | | | | | | | |
| Immuno-Oncology Marker Testing | X | | X | | | | | | | |
| Correlative Studies | | | | | | | | | | |
| Bone Turnover Markers^g (in subjects with bone metastases only) | | Х | Х | | Х | | | X† | | |

^a Each treatment cycle = 3 weeks.

^b Urine pregnancy test is required only in women of childbearing potential.

^c CT or MRI CAP +/- bone scan and RECIST 1.1 assessments will be obtained at baseline and after every 3 cycles. irRECIST = immune-related response criteria. PET/CT is an acceptable alternative imaging modality. All scans can be performed \pm 7 days from the scheduled date.

d Whole Body Bone Scan is required for subjects with known or suspected bone metastases. All scans can be performed \pm 7 days from the scheduled date.

^e The baseline optional fresh tumor biopsy should be obtained during the screening period, prior to C1D1 treatment. The post-treatment optional fresh tumor biopsy should be obtained approximately 3-6 weeks (during cycle 2). Subjects may consent for separately for either baseline and/or post-treatment biopsies.

g Bone turnover markers may include β C-terminal telopeptide (β-CTX), bone specific alkaline phosphatase, and procollagen type 1 amino-terminal propeptide (P1NP). †Bone turnover markers will be collected through cycle 7 but not beyond. Bone tumor markers are not required during the second course of treatment.

ⁱ Total T3 = Total thriiodothyronine, Free T4= T4 (thyroxine) Free

^j Screening labs and pregnancy tests do not need to be repeated at C1D1 if done within 7 days of C1D1.

^k EKG tests will be performed through cycle 7, and then only as clinically indicated.

¹ In the absence of disease progression, pembrolizumab may be administered for up to 35 cycles (first course). If the patient progresses after discontinuing pembrolizumab, they may resume dosing for up to 17 additional cycles (second course), providing they meet criteria for retreatment. See protocol section 5.2.1 for additional information.

^m Survival status: patients will be followed for survival every 6 months (±1 month) for 3 years after completion of study treatment or until study discontinuation, whichever occurs first.

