| | Direct bilirubin \leq ULN for subjects with total bilirubin levels $>$ | | |
| | 1.5 ULN. For subjects with Gilbert's disease $\leq 3 \text{ mg/dL}$. | | |
| AST (SCOT) and ALT (SCDT) | \leq 2.5 X ULN OR | | |
| AST (SOOT) and ALT (SOFT) | \leq 5 X ULN for subjects with liver metastases | | |
| Albumin | $\geq 2.5 \text{ mg/dL}$ | | |
| Coagulation | | | |
| International Normalized Ratio (INR) or Prothrombin Time (PT) | \leq 1.5 X ULN unless subject is receiving anticoagulant therapy as long as PT or PTT is within therapeutic range of intended use of anticoagulants | | |
| Activated Partial Thromboplastin Time (aPTT) | \leq 1.5 X ULN unless subject is receiving anticoagulant therapy as long as PT or PTT is within therapeutic range of intended use of anticoagulants | | |
| Activated Partial Thromboplastin Time (aPTT) ^a Creatinine clearance should be calculated | as long as PT or PTT is within therapeutic range of intended of anticoagulants per institutional standard. | | |

Table 1: Adequate Organ Function Laboratory Values

11. Female participants of childbearing potential should have a negative urine or serum pregnancy within 72 hours prior to receiving the first dose of study medication and should not be breastfeeding. If the urine test is positive or cannot be confirmed as negative, a serum pregnancy test will be required.

12. Female subjects of childbearing potential must be willing to use an adequate method of contraception as outlined in Section 5.5.2 – Contraception, for the course of the study through 120 days after the last dose of study medication.

Note: Abstinence is acceptable if this is the usual lifestyle and preferred contraception for the participant.

13. Male participants of childbearing potential must agree to use an adequate method of contraception as outlined in Section 5.5.2 – Contraception, starting with the first dose of study therapy through 120 days after the last dose of study therapy and refrain from donating sperm during this period.

Note: Abstinence is acceptable if this is the usual lifestyle and preferred contraception for the subject.

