7.1.1.1.2 Inclusion/Exclusion Criteria

All inclusion and exclusion criteria will be reviewed by the investigator or qualified designee to ensure that the subject qualifies for the trial.

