7.1.3 Laboratory Procedures/Assessments

Details regarding specific laboratory procedures/assessments to be performed in this trial are provided below Laboratory Safety Evaluations (Hematology, Chemistry and Urinalysis)

Laboratory tests for hematology, chemistry, urinalysis, and others are specified in Table 10.

Table 10: Laboratory Tests

| Hematology | Chemistry | Urinalysis | Other |
|----------------------------------|---|--|--|
| Hematocrit | Albumin | Blood | Serum β -human chorionic gonadotropin (β -hCG) ² |
| Hemoglobin | Alkaline phosphatase | Glucose | |
| Platelet count | Alanine aminotransferase (ALT) | Protein | PT (INR) |
| WBC (total and differential) | Aspartate aminotransferase (AST) | Specific gravity | aPTT |
| Red Blood Cell Count | Carbon Dioxide | Microscopic exam (If abnormal results are noted) | Total triiodothyronine (T3) |
| Absolute Neutrophil Count | Lactate dehydrogenase (LDH) ¹ | | Free thyroxine (T4) |
| Absolute Lymphocyte Count | Calcium | Urine pregnancy test ² | Thyroid stimulating hormone (TSH) |
| | Chloride | | |
| | Glucose | | |
| | Phosphorus | | |
| | Potassium | | |
| | Sodium | | |
| | Total Bilirubin | | |
| | Direct Bilirubin (If total bilirubin is elevated above the upper limit of normal) | | |
| | Total protein | | |
| | Blood Urea Nitrogen | | |
| 1 LDH only required at screening | • | • | • |

2 Perform on women of childbearing potential only. If urine pregnancy results cannot be confirmed as negative, a serum pregnancy test will be required.

After Cycle 1, pre-dose laboratory procedures can be conducted up to 72 hours prior to dosing. Results must be reviewed by the investigator or qualified designee and found to be acceptable prior to each dose of trial treatment.

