7.1.5.1 Screening Period

All screening evaluations must be completed and reviewed to confirm that subjects meet all eligibility criteria before initiating study treatment. Written informed consent for participation in the study must be obtained before performing any study-specific screening tests or evaluations. Informed Consent Forms for subjects who are not subsequently enrolled will be maintained at the study site.

Screening and pre-treatment tests and evaluations will be performed within 28 days preceding Cycle 1 Day 1 (defined as the day of first dose of study treatment), unless otherwise specified. Results of standard-of-care tests or examinations performed prior to obtaining informed consent and within 28 days prior to study entry may be used; such tests do not need to be repeated for screening.

See the study Schedule of Events (Section 6.0) for schedule of screening assessments.

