7.1.5.2 Treatment Period

All visits must occur within ± 3 days from the scheduled date, unless otherwise noted. All assessments will be performed on the day of the specified visit unless a time window is specified. Assessments scheduled on the day of study treatment administration (Day 1) of each cycle should be performed prior to study drug infusion, unless otherwise noted. C1D1 laboratory assessments do not need to be repeated if screening labs were done within 7 days of C1D1.

See the study Schedule of Events (Section 6.0) for schedule of treatment period assessments.

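### Schedule footnote j accepts a pregnancy test up to 7 days old at first dose, while inclusion criterion 11 requires one within 72 hours

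*Combined protocol and SAP*

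**What the plan says.** Inclusion criterion 11 (Section 5.1.1) says that female participants of childbearing potential "should have a negative urine or serum pregnancy within 72 hours prior to receiving the first dose of study medication".

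In the schedule chart (Section 6.0), the Cycle 1 cell of the urine pregnancy-test row carries footnote j: "Screening labs and pregnancy tests do not need to be repeated at C1D1 if done within 7 days of C1D1".

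Three other provisions bear on the first dose:

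- Section 7.1.5.1 fixes the anchor: "Cycle 1 Day 1 (defined as the day of first dose of study treatment". It also requires that "All screening evaluations must be completed and reviewed to confirm that subjects meet all eligibility criteria before initiating study treatment". Section 7.1.1.1.2 adds that "All inclusion and exclusion criteria will be reviewed by the investigator or qualified designee to ensure that the subject qualifies for the trial".
- Section 7.1.5.2 repeats a 7-day waiver for laboratory work: "C1D1 laboratory assessments do not need to be repeated if screening labs were done within 7 days of C1D1". It makes no exception for the pregnancy test, and does not name it either.
- The note under Table 10 (Section 7.1.3) has a 72-hour rule, but only for later cycles: "After Cycle 1, pre-dose laboratory procedures can be conducted up to 72 hours prior to dosing".

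**The concern.** Both rules govern the same test, in the same women, before the same dose, and they give different limits. Footnote j names pregnancy tests expressly, so the conflict does not depend on stretching a general laboratory rule.

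Staff are likely to follow the chart on the day. Section 5.2.2 has treatment given on Day 1 once the procedures detailed in the chart are done, and Section 7.1.5 refers to the chart for visit requirements. The looser limit therefore sits in the operational instruction and the stricter one in the eligibility list.

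A woman dosed on a test that satisfies the chart but not criterion 11 would be an eligibility deviation produced by the protocol's own text. She would also have had a weaker check for early pregnancy before receiving two drugs that Section 5.5.2 says may harm a fetus. The next scheduled test is at Cycle 2, three weeks later, after one pembrolizumab infusion and up to 21 days of cabozantinib.

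**Working it through.** The plan states no figure to reproduce. The check is a unit conversion and a comparison.

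**Inputs**

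- Eligibility limit: 72 hours before first dose (Section 5.1.1, criterion 11).
- Chart limit: 7 days before C1D1 (Section 6.0, footnote j).
- Common anchor: C1D1 is the day of first dose (Section 7.1.5.1).
- Who is tested: women of childbearing potential only (Section 6.0, footnote b).

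**Gap**

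- Chart limit in hours: 7 × 24 = 168 h.
- Excess over the eligibility limit: 168 − 72 = 96 h.

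**By day, with the test at the same clock time as the dose**

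| Last test | Age at first dose | Footnote j (≤168 h) | Criterion 11 (≤72 h) |
|---|---|---|---|
| Day -3 | 72 h | met | met |
| Day -4 | 96 h | met | not met |
| Day -5 | 120 h | met | not met |
| Day -6 | 144 h | met | not met |
| Day -7 | 168 h | met | not met |
| Before Day -7 | >168 h | not met, repeat at C1D1 | not met |

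The rules disagree from Day -7 to Day -4 and agree elsewhere. If 7 days is counted in calendar days rather than hours, the gap could exceed 96 h by some hours, depending on clock times.

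**Does other text settle it?**

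- The 72-hour rule under Table 10 starts after Cycle 1, so it does not reach the first dose.
- Section 7.1.5.2 does not restore the 72-hour limit. Whether its waiver covers the pregnancy test is unclear: Table 10 lists pregnancy tests among the laboratory tests, but footnote j names labs and pregnancy tests separately.
- The eligibility checks in Sections 7.1.1.1.2 and 7.1.5.1 would lead a site applying criterion 11 to use 72 hours. They say nothing about footnote j.

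With the pregnancy test taken out of the waiver, the oldest acceptable test is 72 h and the excess is 72 − 72 = 0 h.

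**The case against.** The best reply is that a site can comply with both rules. Footnote j only permits omitting a repeat test. It does not say that a 7-day-old test makes a subject eligible. Criterion 11 stands in a list the subject must satisfy, and Section 7.1.5.1 requires every criterion to be confirmed before treatment. That section's 28-day screening window also yields where something else is specified, and Section 7.1 describes the chart as a summary. On this reading the qualifying test is always within 72 hours, and the footnote merely avoids a duplicate on the day.

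Much of that stands. A site that tests within 72 hours breaks no rule, and a site that rigorously confirms criterion 11 will do so. But none of these clauses ranks criterion 11 above footnote j, and a 7-day allowance is wider than is needed to avoid duplicating a test already required within 72 hours.

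Two supporting points carry little weight and are not needed. The chart marks the eligibility review at screening only, so it might be signed off early, but that column runs to Day -1 and so includes Days -3 to -1. Section 7.1.5.2 is ambiguous, as noted above.

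It is also fair to say that the consequence is limited. A negative test within 7 days is still required, pregnancy is an exclusion, contraception is required, and the urine test recurs each cycle. The contraception requirement in Section 5.5.2, however, begins on the day study medication starts (14 days earlier for oral contraception), so it does not clearly cover the days between an older test and the first dose.

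**Conclusion.** The concern holds. Footnote j and criterion 11 conflict by 96 hours, and the documents do not say which prevails. This rests on reading 7 days as 168 hours and on treating criterion 11 as binding. It is worded as what subjects should have, but it appears under requirements for eligibility.

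The claim is that the chart could allow an out-of-window test, not that sites will use one. The 96 hours is a span of time, not a rate of affected women. The documents do not give the number of women of childbearing potential. They are a subset of the 25-55 planned subjects, and only those last tested on about Days -7 to -4 are affected, possibly none.

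The Simon design, DLT evaluability and all planned analyses are unaffected. The matter is subject safety and avoidable eligibility deviations, and it should be corrected.

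**What to change.** Keep the 72-hour limit of criterion 11 and bring the other text into line with it:

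- In footnote j, delete the mention of pregnancy tests and add: *The pregnancy test must be within 72 hours before first dose, per inclusion criterion 11.*
- In Section 7.1.5.2, add: *The 7-day waiver does not cover the pregnancy test.*

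The 7-day waiver stays for the other laboratory tests. The cost is one footnote edit and one added sentence in the next amendment, plus at most one repeat urine test in some women of childbearing potential, at a visit where the chart already lists it.
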